9.5.2 Pregnancy Testing

All women participants of childbearing potential will have a urine or serum pregnancy test (sensitive to 25 mIU/mL beta human chorionic gonadotropin [β -hCG]) performed at each vaccination visit (i.e. Day 1, Month 2, Month 6) per the manufacturer's instructions.

The pregnancy test results must be obtained prior to each study vaccination (on the day the participant is vaccinated). Any participant found to be pregnant at the Day 1 visit will not be allocated and will not participate in the study.

For enrolled participants who become pregnant after receiving one or two study vaccination, study visits and vaccination will be paused until resolution of the pregnancy (e.g. term, elective termination, spontaneous abortion). Study visits and study treatment in pregnant participants will be handled as described in [Table 3](#).

Table 3 Guidelines for Pregnant Participants: Managing Study Visits and Study Vaccinations

Visit where pregnancy is detected.	Action
Day 1	
 Do not enroll participant.
Between Day 1 and Month 2	
 No scheduled visits (excluding Month 1 visit) until resolution of the pregnancy (e.g., term, elective termination, spontaneous abortion). The Month 2 study vaccination should be administered at least 4 weeks following resolution of pregnancy and after normalization of β-hCG levels. The Month 6 study vaccination should be administered 4 months after the Month 2 study vaccination. The Month 7 visit should be conducted 1 month after the Month 6 study vaccination.
Between Month 2 and Month 6	
 No scheduled visits (excluding Month 3 visit) until resolution of the pregnancy (e.g., term, elective termination, spontaneous abortion). The Month 6 study vaccination should be administered at least 4 weeks following resolution of pregnancy and after normalization of β-hCG levels. The Month 7 visit should be conducted 1 month after the Month 6 study vaccination.
After Month 6	
 Continue with scheduled study visits during the pregnancy. Safety follow-up will be conducted after resolution of the pregnancy (e.g., term, elective termination, spontaneous abortion).

9.5.3 Post-vaccination Observation Period (30 minutes)

All participants will be observed for at least 30 minutes after each study vaccination for any immediate reaction with particular attention to any evidence of allergic phenomena. This observation period will be documented in the participant's study chart.

9.5.4 Clinical Laboratory Assessments

Refer to Section 12.4, Appendix 4 for the list of clinical laboratory tests to be performed and to the SoA for the timing and frequency.

- All protocol-required laboratory assessments, as defined in Appendix 4, must be conducted in accordance with the manufacturer's instructions.

- If laboratory values from non-protocol specified laboratory assessments performed at the institution's local laboratory require a change in study participant management or are considered clinically significant by the investigator (eg, SAE or AE or dose modification), then the results must be recorded in the appropriate CRF (eg, SLAB).
- For any laboratory tests with values considered clinically significantly abnormal during participation in the study or within 30 days after the last dose of study treatment, repeat assessments may be performed as determined by the investigator.

9.6 Pharmacokinetics

PK parameters will not be evaluated in this study.

9.7 Pharmacodynamics

Pharmacodynamic parameters will not be evaluated in this study.

9.8 Biomarkers

Biomarkers are not evaluated in this study.

9.9 Future Biomedical Research Sample Collection

Future biomedical research samples will not be collected in this study.

9.10 Visit Requirements

Visit requirements are outlined in Section 2 – Schedule of Activities (SoA). Specific procedure-related details are provided above in Section 9 – Study Assessments and Procedures.

9.10.1 Prerequisites for Vaccination Visits

This section summarizes prerequisites for visits with study vaccinations and specimen collection. Deviations from these prerequisites require consultation between the investigator and the Sponsor and written documentation of the collaborative decision. See the Administrative Binder for a summary of deviations that require documentation in this study.

See the inclusion/exclusion criteria for specific restrictions at Day 1 (see Section 6.1 and 6.2). At the Month 2 and Month 6 study vaccination visits, study personnel should verify by questioning the participant and/or by examination that:

1. The participant has not had a fever, i.e. axillary temperature $<37.1^{\circ}\text{C}$, within the 24-hour period prior to the Month 2 and Month 6 study vaccination visits.
2. The participant has not received any systemic (oral or parenteral) corticosteroids within 2 weeks prior to the Month 2 and Month 6 study vaccination visits.
3. The participant has not received a non-study inactivated or recombinant vaccine within 14 days prior to the Month 2 and Month 6 study vaccination visits or a non-study live vaccine within 21 days prior to the Month 2 and Month 6 study vaccination visits.

4. The participant is not pregnant as confirmed by a urine or serum pregnancy test.

If the participant does not meet the requirements listed above, the study visit (including specimen collection and study vaccination) should be rescheduled.

9.10.2 Discontinued Participants Continuing to be Monitored in the Study

Participants who discontinue study vaccinations but continue in the study may attend study visits per the SoA (Section 2). However, serum will not be collected at the Month 7 study visit from participants who did not complete the 3-dose regimen of study vaccination.

10 Statistical Analysis Plan

This section outlines the statistical analysis strategy and procedures for the study. If, after the study has begun, but prior to any final database lock, changes made to primary and/or key secondary hypotheses, or the statistical methods related to those hypotheses, then the protocol will be amended (consistent with ICH Guideline E-9). Changes to exploratory or other non-confirmatory analyses made after the protocol has been finalized, but prior to final database lock, will be documented in a supplemental Statistical Analysis Plan (sSAP) and referenced in the Clinical Study Report (CSR) for the study. Post hoc exploratory analyses will be clearly identified in the CSR. A full CSR will be generated for Base Stage and a supplemental statistical report will be generated for Extension Stage.

10.1 Statistical Analysis Plan Summary

Key elements of the statistical analysis plan are summarized below; the comprehensive plan is provided in Sections 10.2-10.12.

Study Design Overview	A Phase 3 Open-Label Clinical Trial to Study the Immunogenicity, Safety and Tolerability of Recombinant Human Papillomavirus Quadrivalent (Types 6, 11, 16, 18) Vaccine (V501) in Chinese Girls Aged 9-19 Years and Young Women Aged 20-26 Years.
Treatment Assignment	It is a single-arm, open-label study. All enrolled participants will receive a 3-dose regimen of V501. Stratification factors are provided in Section 7.3.1.
Analysis Populations	Immunogenicity: Per protocol immunogenicity (PPI) population Safety: All Participants as Treated (APaT) population

Primary Endpoint(s)	
Base stage:
 
The primary endpoints are cLIA GMTs to each of HPV 6, 11, 16, and 18 at 1 month post dose 3.
 
Extension stage:
 
• cLIA GMTs and seropositivity percentages to each of HPV 6, 11, 16, and 18 at Month 12, Month 24, Month 36, Month 48, and Month 60.• IgG LIA GMTs and seropositivity percentages to each of HPV 6, 11, 16, and 18 at Month 12, Month 24, Month 36, Month 48, and Month 60.
Secondary Endpoints	
Base stage:
 
The key secondary endpoints are cLIA seroconversion percentages to each of HPV 6, 11, 16, and 18 at 1 month post dose 3.
 
Extension stage:
 
Proportion of participants experiencing SAEs.

Statistical Methods for Key Immunogenicity Analyses	
Base stage:
 
The primary hypotheses (H_1) of non-inferiority of GMTs for each of HPV types 6, 11, 16, and 18 will be addressed by 4 one-sided tests of non-inferiority, with $H_0: \text{GMT}_1/\text{GMT}_2 \leq 0.67$ and $H_a: \text{GMT}_1/\text{GMT}_2 > 0.67$, at $\alpha=0.025$. GMT_1 and GMT_2 represent the GMTs at 1 month post dose 3 in girls aged 9-19 years and young women aged 20-26 years, respectively.
 
Extension stage:
 
GMTs and seropositivity percentages to the each of HPV types 6, 11, 16, 18 will be summarized and plotted.

Statistical Methods for Key Safety Analyses	All safety data will be summarized as frequencies and percentages for the two age groups in the base stage and for the 9-19 years old group in the extension stage.
Interim Analyses	No interim analysis is planned.

Multiplicity	Since success is required on all 4 vaccine HPV types for each of the primary (H1) and secondary (H2) hypotheses, no multiplicity adjustment will be made for the multiple tests within each hypothesis. In addition, no adjustments will be made between primary and secondary hypotheses. No multiplicity will be adjusted for the extension stage.
Sample Size and Power	The planned sample size is 766 participants. Success criterion of the study is the success on the primary hypothesis (H1) of the base stage; the overall power to claim the study success based on H1 is approximately 92% to demonstrate that girls aged 9-19 years is non-inferior to young women aged 20-26 years at an overall one-sided 2.5% alpha-level under the assumptions listed in Section 10.9.1. The sample size of the extension stage is based on the number of participants eligible for entering the extension stage.

10.2 Responsibility for Analyses/In-House Blinding

The statistical analysis of the data obtained from this study will be the responsibility of the Clinical Biostatistics department of the Sponsor.

This trial is being conducted as a single-arm, open-label study, i.e., all participants in this trial will receive V501; participants, investigators, and Sponsor personnel will be aware of participant treatment after each participant is enrolled.

10.3 Hypotheses/Estimation

Objectives and hypotheses of the study are stated in Section 4.

10.4 Analysis Endpoints

10.4.1 Immunogenicity Endpoints

Base stage:

The primary immunogenicity endpoints are cLIA GMTs to HPV 6, 11, 16 and 18 at 1 month post dose 3. The cLIA GMTs to HPV 6, 11, 16 and 18 at Day 1 will also be summarized.

The key secondary immunogenicity endpoints are the cLIA seroconversion percentages to each of HPV 6, 11, 16 and 18 at 1 month post dose 3. Seroconversion is defined as changing serostatus from seronegative at Day 1 to seropositive at 1 month post dose 3. A participant with a cLIA titer at or above the serostatus cutoff value for a given HPV type is considered seropositive for that type.

Anti-HPV 6, 11, 16, and 18 GMTs and seroconversion percentages measured by IgG LIA will be summarized as secondary objective of immunogenicity.

The exploratory endpoints for immunogenicity include GMTs and seroconversion percentages to each of HPV 6, 11, 16, and 18 measured by PBNA, which was developed by NIFDC.

Extension stage:

Anti-HPV GMTs and seropositivity percentages to HPV 6, 11, 16, and 18 at Month 12, Month 24, Month 36, Month 48, and Month 60 measured by cLIA and IgG LIA will be summarized to describe persistence of serum antibody responses to the 4 vaccine HPV types.

The exploratory endpoints for immunogenicity include PBNA GMTs and seropositivity percentages to the 4 vaccine HPV types.

10.4.2 Safety Endpoints

Base stage:

Safety endpoints that will be used to evaluate the safety and tolerability of V501 will include proportions of participants who reported solicited injection-site AEs and solicited systemic AEs within Day 1 to Day 15 after study vaccination, and all AEs within Day 1 to Day 31 after study vaccination. In addition, SAEs occurring at any time during the base stage and maximum axillary temperatures reported from Day 1 to Day 5 after study vaccination will be summarized. Pregnancy outcomes and infants SAEs during the base stage will also be summarized.

Extension stage:

SAEs, pregnancy outcomes, and infants SAEs during the extension stage will be summarized.

10.5 Analysis Populations

10.5.1 Immunogenicity Analysis Populations

Per-Protocol Immunogenicity Population

The per-protocol immunogenicity (PPI) population will serve as the primary population for the analysis of immune response to each of the 4 HPV types (6, 11, 16, and 18). To be included in this population, participants must:

- (1) Have received all 3 study vaccinations with the correct dose of the correct clinical material, and each vaccination visit must occur within the vaccination visit window specified in Section 2 – SoA.
- (2) Be seronegative at Day 1 for the HPV type being analyzed. In the analysis of HPV types 6 and 11, a participant must be seronegative for both HPV types 6 and 11.
- (3) Have provided Month 7 serum sample within the visit window specified in Section 2 – SoA.
- (4) At any time from Day 1 through Month 7, not meet any exclusion criteria that are deemed to potentially interfere with the evaluation of immune response to injections of V501.

All Type-Specific Naïve Participants with Serology (ANPS) Population

A supportive immunogenicity analysis will be carried out on the all type-specific naïve participants with serology population. To be included in this population, participants must:

- (1) Have received all 3 study vaccinations.
- (2) Be seronegative at Day 1 for the HPV type being analyzed. In the analysis of HPV types 6 and 11, a participant must be seronegative for both HPV types 6 and 11.
- (3) Have provided Month 7 serum sample.

Unlike the PPI population, this population will include participants who meet any exclusion criteria that were deemed to potentially interfere with the evaluation of immune responses to injections of V501. In addition, no day ranges on the timing of the vaccination and the collection of Month 7 serum sample will be applied.

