Medical History/ New Medical Condition	X	X	X	X	X	X	X	X	X	X	X	
Base stage: At Day 1, medical history for 1 year prior to Day 1 is collected. After Day 1, new conditions not already recorded as medical history or adverse events are collected. For the participants who have had sexual intercourse, sexual history, lifetime gynecologic history, pregnancy history, and method of contraception are also collected at Day 1. After Day 1, sexual activity/current method of contraception is collected at Month 2, Month 6, and Month 7.
 
Extension stage: Only new medical conditions not already recorded as medical history or adverse events are to be collected.

Review Medications and Non-Study Vaccination	X	X	X	X	X	X	X	X	X	X	X	
Base stage: See Section 9.1.5.
 
Extension stage: Only non-study HPV vaccine mistakenly administered during the extension stage will be collected.

Study Stage	Base Stage (Participants 9-26 years of age)						Extension Stage (Participants 9-19 years of age)					Notes
	Visit 1 Day 1 Vaccination 1	Visit 2 Month 1	Visit 3 Month 2 Vaccination 2	Visit 4 Month 3	Visit 5 Month 6 Vaccination 3	Visit 6 Month 7	Visit 7 Month 12	Visit 8 Month 24	Visit 9 Month 36	Visit 10 Month 48	Visit 11 Month 60	
Study Visit Number/ Title												
Scheduled Day	1	32	62	93	184	215	366	732	1097	1462	1827	
Scheduling Window:	± 0 days	31 to 38 days after Vaccination 1	± 21 days	31 to 52 days after Vaccination 2	± 28 days	31 to 49 days after Vaccination 3	± 28 days	± 28 days	± 28 days	± 28 days	± 28 days	
Perform Physical Examination (Optional)	X											Optional, per investigator's discretion; perform if needed to assess inclusion/exclusion criteria
Pregnancy Testing (Urine or Serum)	X		X		X							Pregnancy testing must be performed prior to each study vaccination in woman participant of childbearing potential according to the manufacturer's instructions. The pregnancy test must be sensitive to 25 mIU/mL β-hCG. Results should be negative prior to vaccination.
Vital Signs Prior to Vaccination	X		X		X							Height and weight are to be measured at Day 1 only. Axillary temperature, pulse rate, respiratory rate, and blood pressure are to be taken prior to each vaccination. If the participant has a fever (defined as an axillary temperature of ≥37.1°C) within the 24-hour period prior to vaccination, the vaccination should be rescheduled after the fever has resolved.

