
 Objective: To evaluate persistence of immune responses induced by V501 in girls 9 to 19 years of age. 	
 cLIA GMTs and seropositivity percentages to each of HPV 6, 11, 16, and 18 at Month 12, Month 24, Month 36, Month 48, and Month 60 IgG LIA GMTs and seropositivity percentages to each of HPV 6, 11, 16, and 18 at Month 12, Month 24, Month 36, Month 48, and Month 60
Secondary	

 Objective: To evaluate the safety of V501 in girls 9 to 19 years of age. 	
 Proportion of participants experiencing SAEs
Exploratory	

 Objective: To summarize persistence of immune responses to HPV types 6, 11, 16, and 18 assessed using PBNA in girls 9 to 19 years of age. 	
 PBNA GMTs and seropositivity percentages to each of HPV 6, 11, 16, and 18 at Month 12, Month 24, Month 36, Month 48, and Month 60

5 Study Design

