6.2 Exclusion Criteria

Participants are excluded from the study if any of the following criteria apply:

The following exclusion criteria are only applicable for the base stage.

Participants enrolled in the 20-26 years old group will not participate in the extension stage, and participants enrolled in the 9-19 years old group who reported overdose or received non-study HPV vaccine during the base stage will be excluded from the extension stage.

Medical Conditions[†]

1. Participant has a fever (defined as axillary temperature $\geq 37.1^{\circ}\text{C}$) within 24 hours prior to the Day 1 vaccination (if the participant meets this exclusion criterion, the Day 1 visit may be rescheduled for a time when this criterion is not met).
2. Participant has a history of severe allergic reaction (e.g. swelling of the mouth and throat, difficulty breathing, hypotension, or shock) that required medical intervention.
3. Participant is allergic to any vaccine component, including aluminum, yeast, or BENZONASETM (nuclease, Nycomed [used to remove residual nucleic acids from this and other vaccines]).
4. Participant with known thrombocytopenia or any coagulation disorder that would contraindicate intramuscular injections.
5. Participant is currently immunocompromised or has been diagnosed as having congenital or acquired immunodeficiency, human immunodeficiency virus (HIV) infection, lymphoma, leukemia, systemic lupus erythematosus (SLE), rheumatoid arthritis, juvenile rheumatoid arthritis (JRA), inflammatory bowel disease, or other autoimmune condition.
6. Participant has a history of splenectomy.
7. Participant has any condition which in the opinion of the investigator might interfere with the evaluation of the study objectives.
8. Participant has a history of recent or ongoing alcohol or other drug abuse. Alcohol abusers are defined as those who drink despite recurrent social, interpersonal, and legal problems as a result of alcohol use.
9. Participant has a history of a positive test for HPV.
10. Participant has any history of abnormal Pap test showing squamous intraepithelial lesion (SIL) or ASC-US, ASC-H, or biopsy showing cervical intraepithelial neoplasia (CIN), adenocarcinoma in situ or cervical cancer.
11. Participant has a history of external genital wart, vulvar intraepithelial neoplasia (VIN), vaginal intraepithelial neoplasia (VaIN), vulvar cancer or vaginal cancer.

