9.1.5.2 Concomitant Medications

The investigator or qualified designee will record medication, if any, taken by the participant during the study as outlined above.

For the specific case where a participant mistakenly receives a non-study HPV vaccine at any time during the study, the non-study HPV vaccine should be documented in the data collection system.

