[†] P=Primary approach; S=Supportive approach.

[‡] Statistical models are described in further detail below:

ANPS = all type-specific naïve participants with serology; CI = confidence interval; GMT = geometric mean titer; PPI = per-protocol immunogenicity.

PBNA results (GMTs and seroconversion percentages) will be summarized as exploratory objective. The PBNA results of the base stage may be summarized in a supplemental report after the data are available.

Extension stage:

Participants in the 9-19 years old group who have completed 3 doses of study vaccination will be followed up to Month 60 to evaluate the persistence of the serum antibody titers for each of HPV 6, 11, 16 and 18 at Month 12, Month 24, Month 36, Month 48, and Month 60. Both cLIA and IgG LIA will be used to measure GMTs and seropositivity percentages.

Table 5 summarizes the immunogenicity persistence analyses for the extension stage.

Table 5 Analysis Strategy for Immunogenicity Variables – Extension Stage

Endpoint/Variable (Description, Time Point)	Primary vs. Supportive Approach [†]	Statistical Method	Analysis Population	Missing Data Approach
cLIA GMTs to HPV 6, 11, 16 and 18 at Month 12, Month 24, Month 36, Month 48, and Month 60	P	Point and 95% CI estimation will be performed by using an ANOVA model; no statistical testing and between group 95% CI will be given.	PPI	Observed data only
cLIA % seropositivity to HPV 6, 11, 16 and 18 at Month 12, Month 24, Month 36, Month 48, and Month 60	P	Point and 95% CI estimation based on exact method; no statistical testing and between group 95% CI will be given.	PPI	Observed data only
IgG LIA GMTs to HPV 6, 11, 16 and 18 at Month 12, Month 24, Month 36, Month 48, and Month 60	P	Point and 95% CI estimation will be performed by using an ANOVA model; no statistical testing and between group 95% CI will be given.	PPI	Observed data only
IgG LIA % seropositivity to HPV 6, 11, 16 and 18 at Month 12, Month 24, Month 36, Month 48, and Month 60	P	Point and 95% CI estimation based on exact method; no statistical testing and between group 95% CI will be given.	PPI	Observed data only
cLIA GMTs to HPV 6, 11, 16 and 18 at Month 12, Month 24, Month 36, Month 48, and Month 60	S	Reverse cumulative distribution curve (RCD) at Month 12, Month 24, Month 36, Month 48, and Month 60	PPI	Observed data only

[†] P=Primary approach; S=Supportive approach.
CI = confidence interval; GMT = geometric mean titer; PPI = per-protocol immunogenicity.

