10.8 Multiplicity

Base stage:

For immunobridging primary (H1) and secondary (H2) hypotheses, success is claimed if hypotheses for all 4 HPV types are met. Therefore, no multiplicity adjustment will be made to account for the multiple HPV types. In addition, no multiplicity adjustment will be made between primary and key secondary hypotheses.

Extension stage:

There is no multiplicity adjustment as there is no hypothesis for the extension stage.

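### The extension persistence analyses keep titers measured after a later non-study HPV vaccine, because the per-protocol exclusion rule stops at Month 7

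*Combined protocol and SAP*

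**What the plan says.** Section 10.5.1 defines a single PPI population by four conditions: three correct doses within window, seronegativity at Day 1 for the type analysed, a Month 7 sample within window, and an exclusion rule. The exclusion rule says a participant must "At any time from Day 1 through Month 7, not meet any exclusion criteria that are deemed to potentially interfere" with the evaluation of the immune response. None of the four conditions looks beyond Month 7.

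Section 10.6.1 says that girls who completed three doses "will be followed up to Month 60 to evaluate the persistence of the serum antibody titers". Every row of Table 5 (cLIA and IgG LIA GMTs, seropositivity percentages and the reverse cumulative distribution curves, Months 12 to 60) names PPI as the population and uses observed data. No extension-specific population is defined. The extension's primary objective in Section 4 is "To evaluate persistence of immune responses induced by V501 in girls 9 to 19 years of age".

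On other HPV vaccines:

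- Section 6.2 states "The following exclusion criteria are only applicable for the base stage", and adds that girls who reported an overdose or "received non-study HPV vaccine during the base stage will be excluded from the extension stage".
- The extension note in the Schedule of Activities (Section 2) reads "Only non-study HPV vaccine mistakenly administered during the extension stage will be collected".
- Section 9.1.5.2 calls for documentation in the case "where a participant mistakenly receives a non-study HPV vaccine at any time during the study".

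Neither recording instruction is tied to any analysis rule.

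**The concern.** The plan treats a non-study HPV vaccine as disqualifying in the base stage but gives the same exposure no consequence once the base stage has ended. A titer drawn after another HPV vaccine is not purely a response to V501, so an analysis that keeps it does not match the stated objective. There are two related gaps.

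- **Between the stages.** The base stage ends at Month 7, but the Schedule of Activities allows extension consent and eligibility review at Month 12. A vaccine received between those visits falls outside both the Section 6.2 bar and the entry criteria in Section 6.1.2.
- **Recording.** The instructions speak only of vaccine given by mistake. Deliberate receipt is not clearly captured, and data missed at the visit may not be recoverable at analysis.

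At stake are the reported Month 12 to Month 60 persistence estimates. H1, H2 and the definition of study success are not affected.

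**Working it through.** **Step 1: what the text does with an exposed girl.** Suppose a girl in PPI receives a non-study HPV vaccine at Month 30.

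| Question | Source | Answer |
|---|---|---|
| Does she leave PPI? | 10.5.1, fourth condition | No; the window closed at Month 7 |
| Does an exclusion criterion now apply? | 6.2 | No; base stage only |
| Is she barred from the extension? | 6.2 | No; the bar covers base-stage receipt |
| Is the vaccine recorded? | Section 2, 9.1.5.2 | Yes, if regarded as given by mistake |
| Are her Month 36, 48 and 60 titers removed or flagged? | 10.6.1, Table 5 | No; observed data are used |
| Is she analysed separately? | 10.10 | No; no extension subgroup analysis |

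**Step 2: whether exposure is possible.** Section 3.1 says V501 is approved in China for women aged 20-45. Girls aged 15 to 19 at Day 1 are about 15 + 5 = 20 to 19 + 5 = 24 at Month 60, so they reach the approved age range during follow-up. Section 9.2.2 also describes a 9-valent HPV vaccine program whose assay covers types 6, 11, 16 and 18. This shows possibility, not frequency.

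**Step 3: the plan's own figures.** There is no sample-size figure for the extension. The nearest are in Section 10.9.1 and Table 6, and they reproduce:

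- HPV 6 and 16: 383 × 0.85 × 0.90 × 0.95 = 278.3, so 278 per group.
- HPV 11 and 18: 383 × 0.90 × 0.90 × 0.95 = 294.7, so 294 per group.
- Two-sample t power (SD 1.2, true ratio 1, margin 0.67, one-sided 0.025): 0.9755 and 0.9812, product over the four types 0.916, as stated.

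These are base-stage figures. Here they supply only n and the SD.

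**Step 4: effect on a GMT.** Let f be the share of analysed girls exposed before a visit, and k the geometric mean factor by which exposure raises their titer at that visit. The mean log titer rises by f × ln k, so the GMT is multiplied by k^f. The documents give neither f nor k, so both are assumed over a range.

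| f (girls out of 278) | k = 2 | k = 10 | k = 20 |
|---|---|---|---|
| 1% (2.8) | 1.007 | 1.023 | 1.030 |
| 2% (5.6) | 1.014 | 1.047 | 1.062 |
| 5% (13.9) | 1.035 | 1.122 | 1.162 |
| 10% (27.8) | 1.072 | 1.259 | 1.349 |

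**Step 5: comparison with sampling error.** The 95% interval of a single GMT extends by a factor of exp(1.96 × 1.2 / √n) each way. That is 1.151 at n = 278 and 1.147 at n = 294, taking the Month 7 SD to hold later and allowing for no extension attrition. The bias exceeds this half-width when f > ln(1.151) / ln k:

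| k | 2 | 5 | 10 | 20 |
|---|---|---|---|---|
| break-even f | 20.4% | 8.8% | 6.1% | 4.7% |

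**Step 6: effect on seropositivity.** Let true seropositivity be s (also assumed), and suppose exposed girls would otherwise have been seropositive as often as the rest. If all of them then test positive, s becomes s + f(1 − s). With s = 80% this gives 80.2% at f = 1%, 81.0% at f = 5% and 82.0% at f = 10%. With s = 95% and f = 10% it gives 95.5%.

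**The case against.** The best case against acting is proportion. The documents describe receipt as a mistake, extension entrants have already had three doses, and nothing suggests an exposed share near 5%. At 1% the GMT moves by 0.7% to 3.0% against an interval of about 15% each way, and attrition would widen that interval further. No decision hangs on it: Section 10.8 says "There is no multiplicity adjustment as there is no hypothesis for the extension stage". Section 10 also lets non-confirmatory analyses be changed in a supplemental SAP before database lock, and such a document may exist unseen. All of this stands and limits the weight of the point. It does not supply the missing rule.

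Three further objections stand in part.

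- The word *mistakenly* could be read as meaning contrary to the study plan, which would cover any outside HPV vaccine. That reading is possible, so the recording point is a request for clarification and not evidence that data will be lost.
- The direction of bias is an inference, not something the documents state. It assumes a further HPV vaccine does not lower titers to the types it contains. A product lacking a given type could leave that type unchanged (k = 1).
- Analysing all observed titers is a legitimate summary, and removing later titers could select on risk or titer. Reporting both analyses, with counts, answers this.

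**Conclusion.** The concern holds. As written, the plan would count any titer drawn after a post-Month 7 HPV vaccine as V501 persistence, in the primary endpoints of the extension. Any resulting bias in the GMT is upward, and seropositivity can only rise or stay the same, provided a further HPV vaccine does not lower antibody levels.

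The size is unknown and may be near zero. It would exceed the sampling error of a GMT only if the exposed share were above about 20% (k = 2), 6.1% (k = 10) or 4.7% (k = 20). Those thresholds rest on assumed k, n = 278 and SD 1.2.

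Confidence is high on the gap in the text; none is claimed on how often the event will occur. The change should be made because it is cheap and because choosing a rule after seeing the titers would be post hoc. It does not threaten the trial's main conclusion.

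**What to change.** 1. In Section 10.5.1 and Table 5, or in the supplemental SAP before database lock, exclude from the primary persistence analysis all serology results on or after the date of any non-study HPV vaccine. This also covers receipt between Month 7 and extension entry.
2. Keep the all-observed analysis as supportive, and report the number of girls and samples removed at each visit.
3. In the Schedule of Activities and Section 9.1.5.2, state that any non-study HPV vaccine received after Month 7 is recorded with its date, whether or not it was given by mistake.

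The cost is one sentence in the analysis plan and one clarification of an existing instruction. A few late samples may be lost from the primary persistence analysis. If no girl receives another HPV vaccine, nothing is lost. The recording change is the more urgent part, because it must be in place while visits are still taking place.
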